5.13.2 Clinical Laboratory Evaluations

Clinical laboratory variables (including serum fasting gastrin) were summarized using descriptive statistics for baseline, post baseline, and change from baseline to post baseline values.

Individual results for clinical hematology and chemistry laboratory tests that were within the predefined laboratory markedly abnormal value (MAV) criteria ([Appendix A](#)) were summarized in tables. All clinical laboratory data were presented in data listings.

The percentages of subjects with elevated gastrin values ≥ 200 pg/mL and ≥ 400 pg/mL were summarized.

The number and percentages of patients with the following elevations in hepatic laboratory tests were summarized:

- ALT or AST $>8 \times$ ULN.
- ALT or AST $>5 \times$ ULN.
- ALT or AST $>3 \times$ ULN in conjunction with elevated total bilirubin $>2 \times$ ULN.

Summaries and listings of laboratory data were presented. MAV tables and listings were presented in the unit specified in the MAV criteria.

5.13.3 Vital Signs

Vital signs were summarized using descriptive statistics for Baseline, post baseline, and change from Baseline to post baseline values.

All individual vital signs that met predefined criteria for MAVs ([Appendix B](#)) were summarized in tables. All vital sign data were presented in data listings.

5.13.4 12-Lead ECGs

ECG results were interpreted using 1 of the following categories: within normal limits, abnormal but not clinically significant, or abnormal and clinically significant. Week 4 ECG assessments were cross-tabulated against the baseline assessment.

All individual quantitative ECG values that met predefined criteria for MAVs ([Appendix C](#)) were listed. All ECG data were presented in a data listing.

5.13.5 Other Observations Related to Safety

Physical examination results were presented in a data listing and weren't summarized.

5.14 Interim Analysis

Not applicable.

5.15 Changes in the Statistical Analysis Plan

After the unblinded results for the primary and secondary endpoints were available an ad hoc sensitivity analysis was performed. This was done since the placebo response was higher than expected and since the p-value for the primary analysis of the primary endpoint was greater than the level of significance by a small amount. The sensitivity analysis doesn't replace the primary analysis but to see if the conclusion was replicated with a different testing method. Additionally, the most frequent AEs were displayed by SOC and PT instead of HLT and PT.

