## **13.1.3 Efficacy Analysis**

The primary efficacy variable will be the percentage of days without daytime or night time heartburn over 4 weeks as assessed by daily eDiary. Comparisons between dexlansoprazole capsules and placebo will be made using a Wilcoxon rank-sum test.

The secondary efficacy variable will be the percentage of days without nighttime heartburn over 4 weeks as assessed by daily eDiary. Comparisons between dexlansoprazole capsules and placebo will be made using a Wilcoxon rank-sum test.

An additional efficacy variable will be the severity of GERD symptoms at Weeks 2 and 4 as assessed by the investigator. The severity of GERD symptoms at Weeks 2 and 4 will be analyzed using a Cochran-Mantel-Haenszel (CMH) test for ordered responses with baseline severity as the stratum. The percentage of days without rescue medication over 4 weeks as assessed by daily eDiary will be analyzed using Wilcoxon rank-sum test.

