4.0 SAMPLE SIZE CALCULATIONS

A total of 200 subjects were planned to be enrolled into this study to ensure 160 subjects with symptomatic nonerosive GERD would complete the study (assuming a 20% dropout rate). The sample size of 80 subjects per treatment group would provide at least 95% power at the 0.05 two-sided significance level to detect a difference of 25% in the mean percentage of days without daytime or nighttime heartburn over 4 weeks between dexlansoprazole capsules (50%) and placebo (25%). The dexlansoprazole and placebo rates were estimated from prior dexlansoprazole study T-GD05-137. The common standard deviation was assumed to be 35%.

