5.10.1 Primary Efficacy Endpoint

The percentage of days with neither daytime nor nighttime heartburn over the 4 weeks of treatment was summarized descriptively. Comparisons between dexlansoprazole capsules and placebo was made using a Wilcoxon rank-sum test. The two-sided p-value was presented for the difference between dexlansoprazole capsules and placebo; the difference was considered statistically significant if the p-value was less than 0.05.

The percentage of days with neither daytime nor nighttime heartburn was calculated for each subject who has at least 1 daytime or nighttime heartburn result (presence or absence of heartburn) during the 4 weeks of treatment (up to last dose day or Day 35 whichever is first) by calculating:

$$\text{Percentage of days with neither daytime nor nighttime heartburn} = \frac{\text{(the days that were heartburn-free during Treatment Period)}}{\text{(Total number of days for which either a daytime or nighttime result was marked during Treatment Period)}} \times 100\%;$$

all entries on a day must be heartburn-free in order for the day to be counted as a day with neither daytime nor nighttime heartburn.

The days with missing diary results for both daytime and nighttime were excluded from the numerator and denominator. If a subject prematurely terminated, the Treatment Period was defined as from first dose date to last dose date + 1 day. If last dose date was missing, then 35 days was imputed as treatment period.

Subgroup Analyses:

Similar descriptive statistics and Wilcoxon rank-sum tests were repeated on the primary endpoint to evaluate the treatment effect within the different baseline subpopulation levels as follows:

- Age (<45, ≥45 to <65, ≥65 years).
- Gender (male, female).
- BMI (<25, 25-<30, ≥30 kg/m²).
- *H pylori* status (positive, negative).
- Overall study drug compliance (<80%, 80-<90%, ≥90%).

Ad Hoc Sensitivity Analysis

Similar descriptive statistics and two sample T-test were repeated on the primary endpoint to evaluate the treatment effect.

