One possible reason for the outcome of this study is random chance. With a type 1 error rate of 5%, this study had a 1 in 20 chance of showing non-significant results when a true treatment difference existed. It is interesting to recall that in the dexlansoprazole pivotal trials, a stronger level of significance ($\alpha=0.0025$) was used and satisfied.

Another possible reason for the outcome may be that the placebo effect is higher among the population sampled in this study than the population sampled in previous dexlansoprazole studies. In this case, the situation is not that the active treatment is disproven as effective, but is that the study wasn't adequately powered to measure the treatment differences. The assumptions for which this study was powered (ie, sample size determination) were based on Study T-GD05-137, in which the mean percentage of days without daytime or nighttime heartburn for subjects taking placebo was 25%; this placebo response rate was similar in the other dexlansoprazole studies that included a placebo arm (Studies T-GD04-082 and T-GD07-170). High placebo response rates have been observed in other studies of symptomatic GERD [1-3]. Chinese subjects who took placebo in Study TAK-390MR_302, however, had a higher placebo response rate (mean percentage of days without daytime or nighttime heartburn was 37%).

A final reason for the outcome of Study TAK-390MR_302 may be that the disease burden of those sampled was not exactly comparable to that of the patients who participated in the US pivotal and supportive studies, which resulted in the higher than expected placebo response.

For at least two of the three possible reasons described here, the lack of statistical significance shown for the primary endpoint in Study TAK-390MR_302 is not because of a lack of treatment effect, but because the study was not adequately powered to detect the treatment differences. The result of the *ad hoc* sensitivity analysis supports this conclusion. The t-test used in the sensitivity analyses is a more statistically powerful test than the Wilcoxon rank sum test, when certain assumptions are met. In the case of a large sample size (eg. 200 subjects), the t-test is robust.

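### SAP 9.1 over-interprets a non-significant primary result: it misstates the chance of missing a true effect and uses a t-test chosen after unblinding to support a largely circular power argument

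*SAP*

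**What the plan says.** Both documents name one primary test. Protocol 13.1.3 states: "Comparisons between dexlansoprazole capsules and placebo will be made using a Wilcoxon rank-sum test". SAP 5.10.1 repeats it with a two-sided 0.05 threshold. SAP 4.0 sized the trial at 80 per arm after 20% dropout and claims "at least 95% power at the 0.05 two-sided significance level". The effect it was sized for is "a difference of 25% in the mean percentage of days without daytime or nighttime heartburn over 4 weeks" (50% against 25%, SD 35).

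The SAP file also reports results. In 7.1 the Wilcoxon test gave p=0.057. Section 5.15 then records: "After the unblinded results for the primary and secondary endpoints were available an ad hoc sensitivity analysis was performed". The reasons given there are a placebo response above expectation and a p-value only slightly over the threshold; it adds that the new test does not replace the primary analysis. Section 5.10.1 describes it under an ad hoc heading: "Similar descriptive statistics and two sample T-test were repeated on the primary endpoint". Its result was p=0.029.

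The Discussion (9.1) offers three possible explanations: chance, a larger placebo effect in this population, and a disease burden unlike that of the US studies. On chance it says that, with a 5% type 1 error rate, "this study had a 1 in 20 chance of showing non-significant results when a true treatment difference existed". It then says that for at least two of the three reasons the non-significance "is not because of a lack of treatment effect, but because the study was not adequately powered to detect the treatment differences", and that the ad hoc result backs this. It adds, subject to a condition on the test's assumptions: "The t-test used in the sensitivity analyses is a more statistically powerful test than the Wilcoxon rank sum test".

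**The concern.** Three steps in 9.1 do not follow.

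- **The error rate.** The type I rate is the chance of a significant result when there is no difference. The chance of a non-significant result when there is one is the type II rate, which depends on how large the true difference is.
- **The t-test as support.** It was chosen after the planned p-value was known, partly because that value was close to 0.05. It analyses the same 215 values, with the same placebo mean, so it says nothing about why placebo did well. Section 5.15 gives its purpose as seeing whether the conclusion is replicated; it was not, because the two tests fall on opposite sides of 0.05.
- **Power as the explanation.** Low power explains a null result only if there is a reason, apart from the result itself, to think the trial could not find the effect it sought.

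At stake is what a reader takes from the trial. The planned analysis leaves the question open; 9.1 offers a reason to treat it as settled in favour of the drug.

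**Working it through.** **Inputs.** Design (SAP 4.0): difference 25, SD 35, 80 per arm, two-sided 0.05, 160 completers of 200. Results (SAP 6.1, 6.3 and Table 7.a): placebo n=108, mean 36.98, SD 31.999; dexlansoprazole n=107, mean 47.21, SD 35.995; 12 of 217 did not complete all visits.

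**1. The plan's power.** SE = 35 × sqrt(2/80) = 5.534. 25/5.534 = 4.518. Power = Φ(4.518 − 1.960) = 99.5%; the noncentral t gives 99.4%. This meets the stated floor of 95%. Enrolment also reproduces: 160/0.80 = 200.

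**2. The reported t-test.** Pooled SD = sqrt[(107 × 31.999² + 106 × 35.995²)/213] = 34.05. SE = 34.05 × sqrt(1/108 + 1/107) = 4.644. Mean difference = 47.21 − 36.98 = 10.23. t = 10.23/4.644 = 2.203, p = 0.0287, matching 0.029. The 95% CI is 1.1 to 19.4. The Wilcoxon p-value cannot be rebuilt without subject-level data.

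**3. The chance of missing a true difference.**
- Planned 25 points, 80 per arm: 100% − 99.4% = about 0.6%. For the Wilcoxon test, assuming an efficiency relative to the t-test of 0.955 or 0.864, power is 99.3% or 98.7%, so a miss is 0.7% or 1.3%.
- Planned 25 points, 108/107, SD 34.05: power 99.97%, so a miss is about 0.03%. With SD 35 it is 0.06%.
- A 1-in-20 miss needs a true difference of (1.960 + 1.645) × 4.644 = 16.7 points, a figure found nowhere in the plan.

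**4. Which planning input failed?**
- Analysed: 215, against 160 planned completers.
- Non-completion: 12/217 = 5.5%, against 20%.
- SD: 34.05, against 35.
- Difference in means: 10.23, against 25.

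Only the difference fell short.

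**5. Power at 108/107, SD 34.05 (noncentral t).**

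| Assumed true difference | Power |
|---|---|
| 25 (planned) | 99.97% |
| 50 − 36.98 = 13.02 (only the placebo mean changed) | 79.7% (77.5% with SD 35) |
| 10.23 (observed) | 59% |

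The higher placebo response alone leaves about 80% power. The clearly low figure appears only when the observed difference is used as the truth. The argument then says no more than that the effect was smaller than planned.

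**6. What choosing the test afterwards can do.** This assumes beta-distributed percentages rounded to a 28-day grid, at 108/107, with 10,000 runs. Accepting either test at 0.05 gives a type I error of 5.5% to 6.3% when both arms share a distribution. With equal means but SDs of 32 and 36 it is 7.7%, where Wilcoxon alone gives 6.2%. The inflation is modest.

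**The case against.** The strongest defence has four parts.

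**Disclosure.** A reader might infer that the t-test was slipped in among the planned methods. The documents do not support that. It is called ad hoc in 5.10.1 and 5.10.2, its timing and motive are in 5.15 and again in 9.1, and the in-text efficacy table was changed to leave it out. Those sections need no relabelling.

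**The conclusions.** A reader might infer that the report turns a failed primary into an efficacy claim throughout. It does not. The synopsis, 7.1, 7.3 and 9.2 all report non-significance, and none of the conclusion sections relies on the t-test. The overreach is confined to 9.1, where the explanations are introduced as possible ones.

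**Power.** A reader might infer that power above 99% for 25 points refutes the sponsor. It does not, because the sponsor's claim is conditional on a higher placebo rate. At 13 points power is about 80%, below the 95% design target. Most of the shortfall is also on the placebo side: 36.98 − 25 = 12.0 of the 25 − 10.23 = 14.8 points. This part stands, and placebo response is a reasonable hypothesis. It does not license saying that the result is not due to lack of effect.

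**The choice of test.** A reader might infer that SDs of 32 and 36 on a 0 to 100 scale disprove the remark that the t-test is more powerful. They do not. The sponsor makes the remark conditional on assumptions, and at the observed means and SDs the beta simulation gives the t-test 59% power against 53% for Wilcoxon. With equal SDs and means of 37 and 50, another simulation of the same kind reversed the order (79% against 84%). The remark depends on the scenario, and in no scenario does it justify choosing a test after seeing the result.

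The 1-in-20 figure might also be defended as the complement of the 95% design power. But the sentence ties it to the type 1 error rate, and 95% was a floor that the design exceeded.

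**Conclusion.** The point holds for SAP 9.1. The error-rate sentence is wrong by definition. At the design effect the type II error was about 0.6% with 80 per arm and below 0.1% with the numbers analysed, not 5%. The claim that non-significance is not due to lack of effect is unsupported, and the t-test cannot support it. The power argument is largely circular: about 80% power after changing only the placebo mean, and 59% only at the observed difference.

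A reader might go further and infer that the trial shows no effect. The documents do not support that either. The t-based interval of 1.1 to 19.4 excludes the planned 25 points but is compatible with a smaller benefit. That interval is post hoc, like the test it comes from.

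The power figures rest on a t approximation and the reported means and SDs. The simulated figures rest on assumed beta distributions.

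**What to change.** Change the wording in SAP 9.1 only:

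- Correct the 1-in-20 sentence. Name the type II error, and say it was about 0.6% at the planned 25 points with 80 per arm and below 0.1% with the 108 and 107 analysed.
- Delete the statement that the result is not due to a lack of effect and the sentence saying that the ad hoc test supports it. Say instead that the pre-planned analysis did not show a difference (p=0.057) and that the data are compatible with a mean effect smaller than the planned 25 points.
- If the placebo-response explanation stays, present it as a hypothesis with its figure: about 80% power at 13 points.
- If the mean difference of 10.2 points (t-based 95% CI 1.1 to 19.4) is given, label it post hoc and attach no significance claim. Printed without that label beside p=0.057, it would recreate the conflict.

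No re-analysis is needed. The cost is the loss of a favourable argument in the report.

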6.0 STUDY RESULTS

6.1 Disposition of Subjects

A total of 325 subjects were screened. Of the subjects screened, 108 (33.2%) were ineligible for entrance into the treatment period. The primary reasons for screen failure were subject did not meet entrance criteria (80.6%), withdrawal by subject (13.9%), and other reasons (5.6%).

Of the subjects screened, 217 (66.8%) entered the treatment period at 20 sites in China: 108 subjects were randomized to the dexlansoprazole capsules group and 109 subjects were randomized to the placebo group. Of note, one subject in each group never received any study drug.

A total of 10 subjects prematurely discontinued study drug, and 205 subjects completed all the study drug and planned study visits.

Overall subject disposition is presented in [Table 6.a](#), and a flow chart is presented [Figure 6.a](#). By-subject listings of screen failures and subject disposition are provided in Appendix 16.2.1.2 and 16.2.1.3.

Table 6.a Overall Disposition of Subjects

	Placebo QD N (%)	Dexlansoprazole 30 mg QD N (%)	Total N (%)
Subject Screened			325
Subjects Eligible for Entrance Into Treatment Period (a)			217 (66.8)
Randomized But Not Treated (b)	1 (<1)	1 (<1)	2 (<1)
Completed Study Drug (b)	102 (93.6)	103 (95.4)	205 (94.5)
Prematurely Discontinued Study Drug (b)	6 (5.5)	4 (3.7)	10 (4.6)
Completed All Planned Study Visits (b)	102 (93.6)	103 (95.4)	205 (94.5)
Did Not Complete All Planned Study Visits (b)	7 (6.4)	5 (4.6)	12 (5.5)
Subjects Not Eligible for Entrance Into Treatment Period (a)			108 (33.2)
Primary Reason Subject not Eligible for Treatment Period (c)			
Adverse Event			0
Significant Protocol Deviation			0
Lost to Follow-up			0
Withdrawal by Subject			15 (13.9)
Study Termination by Sponsor			0
Pregnancy			0
Did not Meet Inclusion Criteria or Did Meet Exclusion Criteria			87 (80.6)
Other			6 (5.6)

[figure not shown]
Source: Table 15.1.3 and Table 15.1.5.

(a) Denominator of the percentage is the number of subjects screened.

(b) Denominator of the percentage is the total number of subjects who are eligible for entrance into treatment period.

(c) Denominator of the percentage is the total number of subjects who aren't eligible for entrance into treatment period.

Figure 6.a Flow Chart of Subject Disposition

6.3 Analysis Sets

A total of 217 subjects were randomized and included in the randomized set: 109 subjects in placebo group and 108 subjects in the dexlansoprazole capsules group. Two subjects were excluded from the safety analysis set and full analysis set because they did not receive study drug (Table 15.1.7). The remaining 215 subjects were included in the safety analysis set and full analysis set: 108 subjects in placebo group and 107 subjects in dexlansoprazole capsules group.

6.4 Demographics and Other Baseline Characteristics

The mean age of the subjects was 44.3 years. More than half of subjects were female. For the number of days with heartburn at baseline, the mean values were similar between treatment groups. And for the mean severity of heartburn at baseline, the mean values were also similar between treatment groups. Detailed demographic and baseline characteristics data are summarized in Table 15.1.8.

6.5 Medical History and Concurrent Medical Conditions

Similar percentages of subjects reported a medical history item across the treatment groups. The most common were Caesarean section (2.3%), hysterectomy (2.3%) and chronic gastritis (2.3%). The incidence for all other medical history items was low (<2%). Details of medical history information are provided in Table 15.1.9 and Appendix 16.2.4.2.

The incidence of concurrent medical conditions was also similar across the treatment groups. The most common concurrent medical condition was chronic gastritis (48.4%) and *Helicobacter* test positive (16.3%). The details of the concurrent medical conditions information are listed in Table 15.1.10 and Appendix 16.2.4.3.

6.6 Medication History and Concomitant Medications

6.6.1 Medication History

The incidence of medication history was similar across the treatment groups. The most common of these medications were propofol (48.8%) and dyclonine hydrochloride (34.9%). The details of medication history information are listed in Table 15.1.11 and Appendix 16.2.4.4.

6.6.2 Concomitant Medications

Concomitant medications included any medication taken which was ongoing as of Study Day 1, ended on or after Study Day 1 or started on or after Study Day 1 and no more than 1 day after the last dose of study drug.

For the concomitant medications that started and stopped prior to baseline, the incidence was similar across the treatment groups, and the most common concomitant medications were propofol: dexlansoprazole capsules group (54.2%) and placebo group (54.6%); dyclonine hydrochloride: dexlansoprazole capsules group (43.0%) and placebo group (34.3%); and hydrotalcite: dexlansoprazole capsules group (29.0%) and placebo group (38.0%).

For the concomitant medications that started prior to and were ongoing at baseline, the incidence in dexlansoprazole capsules group (15.9%) was less than that in placebo group (27.8%), and the most common concomitant medications was hydrotalcite: dexlansoprazole capsules group (3.7%) and placebo group (8.3%).

For the concomitant medications that started after baseline, the incidence in dexlansoprazole capsules group (34.6%) was less than that in placebo group (45.4%), and the most common concomitant medications was hydrotalcite: dexlansoprazole capsules group (15.9%) and placebo group (23.1%).

For the concomitant medications that were ongoing at baseline and those that started after baseline, the incidence in dexlansoprazole capsules group (39.3%) was less than that in placebo group (53.7%), and the most common concomitant medications was hydrotalcite: dexlansoprazole capsules group (16.8%) and placebo group (25.9%).

The details of the concomitant medications information are summarized in Table 15.1.12.1, 15.1.12.2, 15.1.12.3, and 15.1.12.4, and by-subject listing are presented in Appendix 16.2.4.5. The glossary of medication history and concurrent medications by preferred medication name is provided in Table 15.1.13.

6.7 Study Drug Exposure and Overdose

The mean duration of study drug exposure was the same in each treatment group (26.8 days). Mean study drug compliance was high in both groups, with values over 99%. Diary compliance was high in both treatment groups, with 95.74% compliance in the placebo group and 93.84% in the dexlansoprazole group.

The details of study drug exposure and compliance information are summarized in Table 15.1.14 and listed in Appendix 16.2.5.1 and 16.2.5.2.

